### Section 2: Introduction

#### **Background and objectives:**

Achilles tendinopathy is a debilitating injury that is common among athletes, especially those involved in running sports. Around 30% of all runners exhibit Achilles tendinopathy with an annual incidence of 7-9%. Of these patients, roughly one-third will have insertional Achilles tendinopathy (IAT). Several mechanisms are considered to play a role in the etiology of Achilles tendinopathy, yet a prominent role seems present for excessive overload. Traditionally, the nature of this overload is thought to be purely tensile. However, the Achilles tendon can also be exposed to compressive loads at the insertion when the tendon wraps around the posterior prominence of the calcaneus during dorsiflexion of the ankle. The formation of fibrocartilage-like tissue, which is typically found in histological examination of tendinopathy, can be considered as an adaptation to this compressive load, driven by the tenocyte's mechanotransduction process. Therefore, it is recommended to reduce the amount of compressive load on the tendon during rehabilitation while exerting sufficient tensile load. However, these recommendations are mainly based on a pilot study and expert opinion. Therefore, this RCT investigates the effectiveness of low tendon compression rehabilitation (LTCR) with high tendon compression rehabilitation (HTCR) in recreational athletes with IAT. Limiting the amount of tendon compression on the Achilles tendon insertion will be achieved by (1) patient education, (2) heel inserts and (3) an adapted exercise regimen. The specific objectives of this RCT are to investigate whether LTCR results in better outcomes than HTCR in terms of Achilles tendon pain, function and structure.

### Section 3: Study Methods

#### **Trial design:**

- Superiority trial
- Randomized controlled parallel group design
- Assessor blinded
- Single-center

#### **Randomization:**

Randomization will be performed after baseline assessment. Patients will be randomized in a 1:1 ratio to receive either LTCR (interventional) or HTCR (control) treatment. We will use a permuted block randomization technique with a variety in block sizes, in order to reduce potential allocation prediction and to achieve balance in allocations of patients to the intervention and control arm, stratified according to the preinjury activity level of the patients, for which we used the Cincinnati Sports Activity Scale (CSAS) (level 1 or level 2), and tendon pain severity, for which we used the Victorian Institute of Sports Assessment-Achilles (VISA-A) score (<50 or ≥50 points).

**Sample size:**

A sample size calculation was conducted a priori based on the primary outcome measure, the VISA-A score. To detect a clinically significant mean difference of 10 points in the VISA-A score, with 90% power and a standard deviation of 8.4, and with an alpha level of 0.05, a total of 40 participants would be required. This calculation also accounts for a 20% dropout rate.

**Statistical interim analyses:**

No interim analysis for safety, nor for futility and efficacy will be conducted.

**Timing of final analysis:**

All outcomes will be analyzed in August 2024

**Timing of outcome assessments:**

The data will be collected by the researchers at baseline (i.e. T0), 12 weeks post-baseline (i.e. T1), and 24 weeks post-baseline (i.e. T2).

**Section 4: Statistical Principles****Confidence intervals and P values:**

All applicable statistical tests will be performed using a 5% significance level. All confidence intervals presented will be 95% to indicate the precision of the estimates in this RCT.

**Intervention adherence:**

Exercise adherence will be assessed weekly by recording the days patients performed exercises during the preceding week. Global adherence will be calculated as the percentage of completed daily exercises out of the prescribed daily exercises.

**Analysis populations:**

The RCT data will be analysed according to the 'intention-to-treat' principle. This means that patients will be analyzed according to allocated treatment, regardless of any intercurrent event that may occur after randomization.

**Recruitment:**

The CONSORT flow diagram will be used to summarize the number of patients who were assessed for eligibility, approached, consented, randomized and received their allocated treatment. We will also provide reasons for not approaching patients, and reasons of patients who refused to participate.

**Withdrawal/Follow-up:**

We will present data for each follow-up time point on withdrawal and lost to follow-up in the CONSORT flow diagram with numbers and reasons for withdrawal and number included in the analysis.

**Baseline patient characteristics:**

The characteristics of the patients and family carers will be described in terms of age, gender, BMI, training hours per week, duration of complaints, smoking, pathological side, presence of Haglund deformity or calcifications. Baseline patient characteristics will be summarized, both for the control group and the intervention group. The mean and standard deviation or absolute and relative frequencies will be given for the descriptive variables. For these variables, t-tests or Mann-Whitney U tests will be performed for assessing differences between randomized groups on these baseline variables.

**Section 6: Analysis****Hypothesis primary endpoint:**

The LTCR intervention is expected to result in better outcomes in terms of Achilles tendon pain, function, and structure in recreational athletes with IAT compared to the HCTR intervention.

**Primary endpoint and measure:**

Primary endpoint is mean difference in score on the Victorian Institute of Sports Assessment-Achilles (VISA-A) questionnaire at 12 and 24 weeks between LTCR and HCTR. This validated, reliable, self-administered patient-reported outcome evaluates Achilles tendon pain, function, and ability to play sports. The maximum score is 100, with a lower score indicating greater clinical severity.

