**Analysis methods:**

We will explore the data graphically by means of histograms and QQ plot. We will test for differences in mean score at T1 and T2 for the primary and secondary outcomes between the intervention and control groups. Linear mixed-model analyses with a random intercept model will be used for the continuous variables, with treatment, time, and treatment-by-time interaction as independent variables. Additionally, adjustments for potential baseline covariates including age, gender, BMI, symptom duration, CSAS, VISA-A, and presence of an associated Haglund's deformity and/or retrocalcaneal bursitis will be made. Estimated marginal means with corresponding 95% CI will be reported at baseline and follow-up, both for the intervention and control group. Moreover, the estimated mean difference between the LTCR and HTCR group at T1 and T2 will be reported with 95% CI. Relationships between categorical variables will be analyzed using Fisher's exact test. Patient satisfaction was dichotomized into satisfied (excellent/good) and dissatisfied (moderate/poor). Return to sport was dichotomized into return to the desired sport and no return to desired sport. Differences in exercise adherence between the intervention and control groups will be assessed by a t-test.

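### VISA-A at 12 weeks and at 24 weeks are both primary and each is tested at 5%, with no deciding visit, success rule or testing order, while the sample size covers one comparison

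*SAP*

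**What the plan says.** - **Primary endpoint and measure (Section 6):** the endpoint is the mean difference on the VISA-A "questionnaire at 12 and 24 weeks between LTCR and HCTR". These are two contrasts, and neither is given precedence.
- **Analysis methods (Section 6):** "We will test for differences in mean score at T1 and T2 for the primary and secondary outcomes". The model is a random-intercept linear mixed model "with treatment, time, and treatment-by-time interaction as independent variables", plus baseline covariates. No single term or contrast is named as the primary test. The output is one contrast per visit: "the estimated mean difference between the LTCR and HTCR group at T1 and T2 will be reported with 95% CI".
- **Confidence intervals and P values (Section 4):** "All applicable statistical tests will be performed using a 5% significance level". There is no split of alpha and no multiplicity adjustment.
- **Hypothesis primary endpoint (Section 6):** LTCR is "expected to result in better outcomes in terms of Achilles tendon pain, function, and structure". No visit is named.
- **Sample size (Section 3):** one 10-point VISA-A difference, "with 90% power and a standard deviation of 8.4, and with an alpha level of 0.05", giving 40 participants including 20% dropout. The visit to which the difference and SD apply is not stated, nor is the sidedness of the test.

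**The concern.** The SAP settles the endpoint, the tests and the significance level, and together these produce two primary tests without a rule for combining them. If 12 weeks is significant and 24 weeks is not, or the reverse, the SAP cannot say whether this superiority trial succeeded. The rule would then be chosen with the results in view.

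The two obvious rules have different consequences. If either visit suffices, the chance of at least one false rejection exceeds 5%. If both are required, alpha is safe but power is that of two tests passed together, whereas the trial was sized for one.

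**Working it through.** **Inputs from the SAP.** Difference 10, SD 8.4, alpha 0.05, power 90%, dropout 20% (Sample size); 1:1 allocation (Randomization); two primary visits (Primary endpoint and measure).

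**Assumptions not in the SAP.** Two-sided testing; the same 10-point effect and SD at both visits; T1-T2 correlation ρ of 0.5, 0.7, 0.8 or 0.9.

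**Step 1: reproduce N = 40.** For a two-sample t-test the noncentrality is δ / (σ√(2/n)).
- n = 16 per arm: 10 / (8.4 × √(2/16)) = 3.37, against a critical t of 2.04 on 30 df. Power is 90.3%.
- n = 15 per arm: power is 88.2%, so 16 is the smallest n that reaches 90%.
- 2 × 16 = 32 evaluable; 32 / (1 − 0.20) = 40, exactly the stated total.
- A one-sided test at 0.05 would need 13 per arm: 26/0.8 = 32.5, so 33 or 34 in total. That does not reproduce 40.

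The stated N is therefore the size for one two-sided comparison at 5%.

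**Step 2: either visit suffices.** Family-wise error = 1 − P(|Z₁| < 1.96 and |Z₂| < 1.96), with (Z₁, Z₂) bivariate normal with correlation ρ.

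**Step 3: both visits required.** Joint power = P(both t-tests significant in favour of LTCR), by simulation of two-sample t-tests.

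| ρ | Family-wise error, either suffices | Ratio to 5% | Joint power, 16 per arm at both visits | Joint power, 20 at T1 and 16 at T2 | Joint power, 20 per arm at both visits |
|---|---|---|---|---|---|
| 0.5 | 9.07% | 1.81 | 83.6% | 87.4% | 92.2% |
| 0.7 | 8.35% | 1.67 | 84.9% | 88.1% | 92.9% |
| 0.8 | 7.81% | 1.56 | 85.8% | 88.3% | 93.3% |
| 0.9 | 7.04% | 1.41 | 87.1% | 89.2% | 94.0% |

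The column with 16 per arm at both visits is the SAP's own sizing basis: an unadjusted comparison with the full 20% loss. The other two show later dropout and no dropout.

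**Step 4: allow for baseline adjustment.** With ANCOVA on baseline VISA-A alone, 16 per arm, 8.4 taken as the unadjusted SD and ρ from 0.5 to 0.9, joint power is:
- 85.7% to 88.9% at a baseline/follow-up correlation of 0.3;
- 88.6% to 91.2% at 0.4;
- 92.4% to 94.1% at 0.5.

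**Step 5: compare remedies at 16 evaluable per arm.**
- *Fixed sequence* (named visit at 5%, the other only if the first is significant): type I error is 5.0% with no effect at either visit, and power is 90.3% for the named visit. If only the first visit has the 10-point effect, a false rejection at the second occurs in 3.0% to 3.9% of trials.
- *Bonferroni* (2.5% at each visit): power per visit falls to 83.7%. Restoring 90% needs 19 per arm, and 38/0.8 = 47.5, so 48 in total.

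**The case against.** The strongest reply has four parts.

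1. *Nothing says that either visit suffices.* The word joining the two visits can be read as requiring both, and alpha then holds. That is a fair reading, but the SAP does not state it. The inflation is conditional on the rule, and the absence of the rule is the defect.

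2. *The error rate counts both directions.* The 7.0% to 9.1% includes false findings for either arm, while the hypothesis favours LTCR. By symmetry, the chance of a false claim for LTCR is about half: 4.5% at ρ = 0.5 and 3.5% at ρ = 0.9, against a nominal 2.5%. This is correct and should be borne in mind when quoting the figures. The ratio of 1.4 to 1.8 is unchanged.

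3. *The power shortfall may not exist.* The planned model adjusts for baseline VISA-A, and a mixed model uses the T1 data of later dropouts. Steps 3 and 4 show joint power reaching 90% or more under plausible conditions. This stands, so the shortfall is a conditional consequence and not the main point. The figures also come from t-tests and a simple ANCOVA, not from the full mixed model. The mixed model accounts for the correlation between visits but does not adjust two separate contrasts that are each judged at 5%.

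4. *Both differences will be reported with 95% CIs.* An unfavourable visit therefore cannot be hidden. That limits selective reporting, but it does not say which result decides the trial.

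**Conclusion.** The concern holds and should be fixed before the analysis. The SAP sets two primary tests at 5% each with no deciding visit, success rule, testing order or adjustment, and its N of 40 is exactly that for one two-sided test.

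If either visit is allowed to carry the claim, the two-sided family-wise error is 7.0% to 9.1% for a T1-T2 correlation between 0.9 and 0.5. If both are required, alpha is controlled and joint power is 83.6% to 87.1% on the sizing basis, though it could reach 90% or more with baseline adjustment or lower dropout. These figures rest on the assumed correlations, on two-sided testing and on the same effect and SD at both visits. The finding that the decision rule is missing rests on none of them.

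**What to change.** Before any comparison of outcomes by arm, add one or two sentences to the SAP:

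- Name one VISA-A visit, at the sponsor's choice, as primary and test its between-group contrast from the mixed model at two-sided 5%.
- Test the other visit at two-sided 5% only if the first is significant.
- Report both differences with 95% CIs whatever the outcome.

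The Sample size section should also say that the 10-point difference and SD of 8.4 refer to the named visit, since the 90% power claim depends on it.

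N stays at 40, the family-wise error is held at 5%, and the named visit keeps the power for which the trial was sized. The cost is that no claim can be made at the second visit if the first fails.

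Other rules would also be valid if stated in advance. Requiring both visits needs no change to alpha or N, but the sponsor would have to accept or justify the joint power. Splitting alpha equally would lower power to 83.7% per visit, or raise N to 48 to keep 90%.

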**Secondary endpoints and measures:**

The secondary endpoints were mean difference at 12 and 24 weeks in:

- Patient satisfaction, which is categorized as excellent, good, moderate, or poor.
- Return to sports rate, which is categorized as return to desired sports at pre-injury level; return to desired sports but not at pre-injury level; return to sports but not the desired sports; and no return to sports.
- Visual analogue scale (0-100 mm) for pain during daily activities over the past 7 days
- Visual analogue scale (0-100 mm) for pain during 10 unilateral hops
- Score on the lower extremity functional scale questionnaire. Total score ranges from 0 to 80, where a higher score indicating better lower limb function.
- Score on Tampa scale for kinesiophobia questionnaire. Total score ranges from 17 to 68, where the lowest 17 means no kinesiophobia.
- Score on the EQ-5D-5L questionnaire. Total score ranges from -0.59 to 1, where 1 is the best possible health state.
- Achilles tendon insertion anteroposterior diameter, assessed by ultrasonography in longitudinal view (5 mm distal from the posterosuperior calcaneal border).
- Achilles tendon insertion doppler signal (modified Ohberg Scale; 0-4), assessed by ultrasonography.
- Heel-rise endurance test
- Exercise adherence rate

**Analysis methods:**

We will explore the data graphically by means of histograms and QQ plot. We will test for differences in mean score at T1 and T2 for the primary and secondary outcomes between the intervention and control groups. Linear mixed-model analyses with a random intercept model will be used for the continuous variables, with treatment, time, and treatment-by-time interaction as independent variables. Additionally, adjustments for potential baseline covariates including age, gender, BMI, symptom duration, CSAS, VISA-A, and presence of an associated Haglund's deformity and/or retrocalcaneal bursitis will be made. Estimated marginal means with corresponding 95% CI will be reported at baseline and follow-up, both for the intervention and control group. Moreover, the estimated mean difference between the LTCR and HTCR group at T1 and T2 will be reported with 95% CI. Relationships between categorical variables will be analyzed using Fisher's exact test. Patient satisfaction was dichotomized into satisfied (excellent/good) and dissatisfied (moderate/poor). Return to sport was dichotomized into return to the desired sport and no return to desired sport. Differences in exercise adherence between the intervention and control groups will be assessed by a t-test.

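### Continuous secondary outcomes: the reported T1 and T2 arm differences are not adjusted for the outcome's own T0 value

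*SAP*

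**What the plan says.** SAP Section 6, Analysis methods, sets one model: "Linear mixed-model analyses with a random intercept model will be used for the continuous variables, with treatment, time, and treatment-by-time interaction as independent variables". T0 is one of the time points in the response, because "Estimated marginal means with corresponding 95% CI will be reported at baseline and follow-up, both for the intervention and control group". The treatment effect to be reported is the level difference at each follow-up: "the estimated mean difference between the LTCR and HTCR group at T1 and T2 will be reported with 95% CI". The same covariates apply to all continuous outcomes: "adjustments for potential baseline covariates including age, gender, BMI, symptom duration, CSAS, VISA-A, and presence of an associated Haglund's deformity and/or retrocalcaneal bursitis". No term for the outcome's own T0 value is named, and nothing restricts the arms to a common mean at T0.

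The secondary endpoints (Section 6, Secondary endpoints and measures) include "Achilles tendon insertion anteroposterior diameter, assessed by ultrasonography in longitudinal view", two VAS pain scores, LEFS, Tampa, EQ-5D-5L and the heel-rise test. Under Section 3, Timing of outcome assessments, data are collected at T0, 12 weeks and 24 weeks. Adherence is handled separately: "Differences in exercise adherence between the intervention and control groups will be assessed by a t-test".

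Randomization (Section 3) is stratified by CSAS level and by VISA-A below 50 or not. It is not stratified by any secondary outcome.

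**The concern.** Having T0 in the model looks like baseline adjustment, but here it is not. With a treatment effect, a time effect and their interaction, each arm has its own mean at T0, T1 and T2. The T1 contrast then compares the two T1 means, and the T0 means have no bearing on it. A patient's starting value would help only if it entered as a covariate or if the arms shared one T0 mean.

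Tendon structure is one of the three objectives in Section 2, and insertion diameter is its continuous measure. A tendon that starts thicker is likely to stay thicker. With 20 patients per arm (16 after the planned dropout), a chance gap in starting thickness can appear as a structural treatment effect or hide one, and the intervals are wider than the collected data allow. Baseline VISA-A measures symptoms and function, so there is little reason to expect it to stand in for starting thickness.

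**Working it through.** **The plan's own figure.** The SAP states no sample size, SD or correlation for any secondary outcome. Its total for VISA-A does reproduce. A two-sample t-test with difference 10, SD 8.4, two-sided alpha 0.05 and 90% power needs 15.85, so 16 per arm; 16/(1 − 0.20) = 20 per arm, 40 in total. The checks below use 20 and 16 per arm.

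**Assumption.** Let r be the correlation between an outcome's T0 and follow-up values. The SAP gives none, so r runs from 0.3 to 0.9, with unit SD.

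**Step 1: what the planned contrast is.** The model was fitted without covariates to 40 simulated complete data sets (20 per arm, r = 0.8). The T1 difference equalled the raw T1 mean difference (largest gap 7e-15), with mean SE 0.315 against √(2/20) = 0.316.

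**Step 2: how much variance own-T0 adjustment could remove.** The variance relative to the unadjusted difference is 1 − r², so the share removed is r². For SE at 20 per arm the formula is √(2/n) · √(1 − r²) · √(1 + 1/(2n − 4)). Power is for a 0.5 SD difference, a target assumed here because the SAP sets none.

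| r | variance removed | SE, 20 per arm | power, 20 per arm |
|---|---|---|---|
| no adjustment | – | 0.316 | 34% |
| 0.3 | 9% | 0.306 | 36% |
| 0.5 | 25% | 0.278 | 42% |
| 0.6 | 36% | 0.256 | 48% |
| 0.7 | 49% | 0.229 | 57% |
| 0.8 | 64% | 0.192 | 72% |
| 0.9 | 81% | 0.140 | 94% |

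At 16 per arm, power is 28% without adjustment, against 39% at r = 0.6 and 87% at r = 0.9. The table sets the listed covariates to zero effect, so these gains are upper bounds.

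**Step 3: with a covariate in the model.** Simulation with 16 per arm and 300 runs per r, with one baseline covariate correlated 0.2 with T0 in the role of VISA-A. Carry-over is the slope of the estimated T1 difference on the chance T0 gap. Variances are relative to the SAP contrast.

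| | r = 0.5 | r = 0.7 | r = 0.9 |
|---|---|---|---|
| Carry-over, SAP contrast | 0.50 | 0.62 | 0.86 |
| Carry-over, own T0 as covariate | 0.04 | −0.05 | 0.02 |
| Carry-over, common T0 mean | 0.03 | −0.06 | 0.03 |
| Carry-over, change from T0 | −0.46 | −0.35 | −0.06 |
| Variance, own T0 as covariate | 0.72 | 0.56 | 0.24 |
| Variance, common T0 mean | 0.71 | 0.56 | 0.22 |
| Variance, change from T0 | 0.92 | 0.68 | 0.22 |

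With a moderately correlated covariate instead, carry-over at r = 0.8 was still about 0.6, and about zero after own-T0 adjustment.

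**Step 4: if the listed covariates predict well.** Suppose they explain half of the between-patient variance. Under a random intercept the remaining correlation is (r/2)/(1 − r/2). At r = 0.6, 0.7 and 0.8 this is 0.3/0.7 = 0.43, 0.35/0.65 = 0.54 and 0.4/0.6 = 0.67. Squared, own T0 then removes 18%, 29% and 44% of the variance, rather than 36%, 49% and 64%.

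**Step 5: size of the chance gap.** At 20 per arm the T0 difference between arms has an SD of 0.32 SD units. At r = 0.8 with no covariates, 0.8 × 0.32 ≈ 0.25 SD of that passes into the T1 difference.

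**The case against.** The strongest reply is that the plan is not blind to T0. Arm means at baseline will be reported, so a gap will be visible. The treatment-by-time term in the same fit compares change from T0. The covariate list is worded as open, so own-baseline adjustment is left unspecified, not excluded. The stated model also carries seven covariates, and VISA-A, which covers pain and function, plausibly predicts the VAS and LEFS scores.

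Part of this stands. The gain is smaller where the covariates predict the outcome, which is why the figures above are upper bounds. The rest does not settle the matter. Seeing a gap does not adjust for it. The change contrast is not the effect the SAP says it will report, and it over-corrects when r is low (slope −0.46 at r = 0.5). An open list lets the choice be made after the data are seen, when the raw, change and adjusted differences may disagree.

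A reader might infer more than the document supports:
- **That most of the precision is lost.** More than half the variance is recoverable only if r exceeds about 0.71, and the SAP gives no r. A high value that is plausible for tendon thickness cannot be assumed for pain, kinesiophobia or quality of life.
- **That the whole baseline gap passes into the result.** About r times the gap does. Under randomisation the estimate is unbiased on average, and its interval already includes this variation.
- **That every continuous secondary outcome is affected.** Adherence has no T0 value and is compared by t-test.

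**Conclusion.** The point holds in a limited form. For insertion diameter, both VAS scores, LEFS, Tampa, EQ-5D-5L and heel-rise, the differences the SAP will report at T1 and T2 are not adjusted for the outcome's own T0 value, although that value is to be collected. The consequence is lost precision and conditional bias of roughly r times the chance gap. The recoverable variance runs from about 9% at r = 0.3 to 81% at r = 0.9 at most, and is lower where the listed covariates already predict the outcome.

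This rests on reading the baseline marginal means as placing T0 in the response, on these outcomes being measured at T0, and on assumed correlations. It concerns secondary outcomes only. The VISA-A sample size is untouched. It is a free improvement, not a fault that invalidates the analysis.

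**What to change.** Add to SAP Section 6, Analysis methods: *For each continuous secondary outcome measured at T0, the T1 and T2 differences between arms are adjusted for the T0 value of that same outcome.* Name one method:

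- **Preferred:** keep T0 as a response and constrain the arms to a common mean at T0, by dropping the treatment main effect and keeping arm-specific terms at T1 and T2.
- **Alternative:** take T1 and T2 as responses with the outcome's own T0 value as a covariate.

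Keep CSAS and VISA-A as covariates, since they are the stratification factors. Leave adherence as it is.

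The cost is a short SAP edit and a re-specified SPSS mixed model, with no new data. Neither method yields separate model-based T0 means by arm: the first gives one common value and the second gives none. The promise of baseline marginal means for each arm should therefore become a descriptive table of T0 means. The covariate version drops patients without a T0 value; these should be few, because Section 3 places randomisation after the baseline assessment.
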